**Table 3 PK Draw Timing**

| Visit   | Target Day | Nominal Time   |
|---------|------------|--|
| Visit 2 | Day 1      | 
 
At Predose and 2 hours postdose
 
  |
| Visit 3 | Day 8      | 
 
At Predose and 2 hours postdose
 
  |
| Visit 4 | Day 15     | 
 
At Predose and 2 hours postdose
 
  |
| Visit 5 | Day 28/ET  | 
 
Subgroup 1: One sample predose and one sample at 0.5 to 2.5 hours post application
 
Subgroup 2: One sample at 2.5 to 5 hours post application and one sample at least 2 hours later
 
Subgroup 3: One sample at 5 to 8 hours post application and one sample at least 2 hours later (prior to the subsequent application)
 
 |

### 10.1.2. Baseline

Baseline is defined as the last, non-missing measurement, before or on the date of first administration of study medication.

### 10.1.3. Change from baseline

Change from baseline (CFB) will be calculated as (post-baseline – baseline). CFB will be calculated for patients with both a baseline and post-baseline value as applicable.

Percent CFB will be calculated as (CFB/baseline)\*100, where applicable.

If a baseline value has not been recorded for a parameter, then CFB will not be calculated for that parameter.

## 11. Interim Analyses

No interim analysis will be conducted.

## 12. Statistical Methods

All analyses will use SAS version 9.4 or higher.

Categorical variables will be summarized using counts and percentages based on the specified population total. Percentages will be rounded to one decimal place, except 100% will be displayed without any decimal places and percentages will not be displayed for zero counts.

Continuous data will be summarized using non-missing observations (n, mean, standard deviation (SD), median, Quartile 1, Quartile 3, minimum, and maximum). The median, minimum, and maximum values will be displayed to the same level of the precision as the raw value. Mean, median, Q1 and Q3 will be rounded to 1 decimal place greater than the precision of the original value. The SD will be rounded to 2 decimal places greater than the precision of the original value. Confidence intervals, least square mean (LSM) and standard error (SE) will be provided as appropriate. Confidence intervals, LSM will present the same precision as the mean value whereas SEs will present the same precision as SD.

P-values will be rounded to 3 decimal places. P-values less than 0.001 will be presented as “<0.001” and p-values greater than 0.999 will be presented as “>0.999.”

Statistical hypothesis testing will be one-sided and carried out at the 5% level of significance. Testing will be performed on the primary endpoint and secondary endpoints as appropriate. No adjustments for multiplicity will be made.

If there is strong collinearity between the baseline EASI score/BSA score/IGA score and the baseline severity of AD (moderate versus severe), the continuous baseline score will be included the efficacy analysis.

All the listings will be displayed by treatment arm, patient identifier and date of assessment. Age, gender, and race will be presented on each listing.

### 12.1. Patient Disposition

#### 12.1.1. Disposition

The number of patients screened, randomized, randomized and treated, randomized and not treated, and the number of patients in the analysis sets will be summarized for all screened patients.

The number and percentage of patients will also be summarized for the following patient disposition categories:

1. Completed study drug treatment PP
2. Discontinued study drug early and the reason for discontinuation
3. Completed the study including PTFU
4. Discontinued from the study early and the reason for discontinuation

The table will be presented by treatment arm using the FAS.

All patient's disposition data will be listed.

#### 12.1.2. Important Protocol Deviations

As a guideline, important protocol deviations (IPDs) are:

- Non-compliance with study drug
- Pregnancy
- Other deviations that violate inclusion or exclusion criteria
- Outside Study Windows

Important protocol deviations will be listed.

## 12.2. Demographic and Baseline Characteristics

### 12.2.1. Demographics

Baseline data will be summarized for continuous and categorical variables as applicable.

The following demographic and baseline characteristics will be summarized for the FAS by treatment arm and overall:

- Sex (female, male)
- Race (White, Black or African American, Asian, American Indian or Alaska Native, Native Hawaiian or other Pacific Islander, other)
- Ethnicity (Hispanic or Latino, not Hispanic or Latino)
- Age (years), as continuous variable and Age groups ( $\geq 18$  years to  $<30$  years,  $\geq 31$  years to  $<40$  years,  $\geq 41$  years to  $<50$  years,  $\geq 51$  years to  $<65$  years,).
- Height at baseline (cm)
- Weight at baseline (kg)
- Body mass index at baseline ( $\text{kg}/\text{m}^2$ ) defined as Weight (kg)/[Height (m)]
- Child-bearing potential
- Fitzpatrick skin type
- Baseline AD severity (moderate vs severe)

Demographic and baseline characteristics will also be listed. No statistical testing will be performed on the aforementioned demographic data.

### 12.2.2. Medical History

Medical history will be summarized by treatment arm and overall for all patients in the FAS. Medical history data will be coded using Medical Dictionary for Regulatory Activities (MedDRA) 220 and summarized by system organ class (SOC) and preferred term (PT). No inferential testing will be performed in this section. Medical history data will be presented in a data listing.

## 12.3. Treatments

### 12.3.1. Prior, Concomitant and Prohibited Medications

Medications that stop prior to the first dose of study drug will be classified as prior medication. Medications that start on or after the first dose of study drug until the Day 42/PTFU visit will be classified as concomitant. If a medication starts before the first dose of study drug and stops on or after the first dose of study drug, then the medication will be classified as both prior and concomitant.

Medications will be categorized by medication group and subgroup according to World Health Organization Drug Dictionary Enhanced (WHODRUG 2017JUL DDE B2).

For any medications/nondrug therapies taken from 3 months before the screening visit until the end of the PTFU, inclusively, the medication name, the start and stop date, dose, unit, frequency, route of administration, and indication will be recorded.

Use of any of the following treatments is prohibited during the study:

- Phototherapy (ultraviolet A, ultraviolet B, or psoralen and ultraviolet A therapy)
- Systemic biologic immunosuppressant or immunomodulatory therapy (e.g., etanercept, alefacept, infliximab, dupilumab)
- Non-biologic immunosuppressants (e.g., methotrexate, retinoids, calcineurin inhibitors, cyclosporine, hydroxycarbamide [hydroxyurea], azathioprine)
- Janus kinase (JAK) inhibitors (systemic and topical)
- Systemic or topical corticosteroids (intranasal, inhaled, and topical ocular corticosteroids are allowed if used to treat other medical conditions)

- Cytostatic agents
- Crisaborole
- Systemic antibiotics
- Topical treatments for AD (corticosteroids, calcineurin inhibitors, topical H1 and H2 antihistamines, topical antimicrobials, and other medicated topical agents)
- Live attenuated vaccine treatment
- Other investigational products
- Use of potent inhibitors of cytochrome P450 3A4 such as (but not limited to) clarithromycin, erythromycin, diltiazem, itraconazole, ketoconazole, ritonavir, verapamil, goldenseal, and grapefruit

In order to flag prohibited medications taken in the study, each medication taken will be compared against the list of the prohibited medications the clinical medical officer provided after reviewing the concomitant medication database. Prior, Concomitant and Prohibited medications will be summarized based on the number and percentage of patients using each medication along with the number and percentage of patients using at least one medication within each medication group and subgroup.

Missing or partial medication start/stop date will be imputed as described in [Appendix 4](#). A conservative approach will be used when flagging medications. The medication will be classified as concomitant when a decision is unable to be made even with imputed start/stop medication date.

Prior, Concomitant and Prohibited medications will be summarized for the FAS by treatment arm and overall. Medication data will also be presented in a data listing.

### 12.3.2. Extent of Study Drug Exposure

The duration of exposure to study drug, number of days dosed is taken and compliance with study drug dosing will be summarized by treatment arm using the FAS. Study drug accountability including the weight of the dispensed and returned bottles will be listed. Study drug not returned will be assumed to have been taken.

Study drug compliance (percentage) will be derived using values from the Patient Diary as shown below:

$$[\# \text{ of days patient reported taking study drug} / \# \text{ of days patient was in the study}] * 100\%$$

The descriptive statistics of the continuous study drug compliance will be summarized by treatment group and overall. Days with missing patient diary data will not be included in the calculation above. Percentage of patients meeting Study Drug Compliance will be presented in the following categories: < 80%, ≥ 80% to < 90%, ≥ 90% to < 100%, ≥ 100% to < 110%, ≥ 110% to < 120%, and ≥ 120%.

Major non-compliance is defined as compliance < 80% or compliance > 120%.

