A total of approximately 50 patients who meet all the entry criteria will be randomized on Day 1 via an interactive voice/web response system (IXRS) to ATI-1777 or vehicle treatment in a 1:1 ratio. Patients will be stratified at randomization by severity of AD (moderate versus severe). The study is randomized and double-blinded with regard to ATI-1777 and vehicle in order to prevent bias in treatment allocation and in the assessment of treatment effect. The investigator, site personnel, the sponsor, and their representatives involved in monitoring and conducting the study, and the patients will be blinded to the study medication administered. See [Section 7.3](#) for further details on the

method of assigning patients to the treatment groups, and [Section 7.2](#) for details on access to the treatment codes in the event of emergency unblinding.

During the Treatment Period, patients will apply study drug (ATI-1777 topical solution 2.0% w/w or vehicle) twice daily for 28 days to target areas affected by AD. Patients will be trained by site personnel on how to appropriately apply the study medication. See [Section 7.4](#) for further details on the dose and administration of ATI-1777 and vehicle.

On Day 1 of the study, patients will apply drug in the clinic. The application site will be assessed for serious or severe local AEs prior to discharge from the clinic. Subjects will be informed to contact the site if a severe or serious event occurs. Subjects will be asked to pay particular attention to any events in the first 24 hours after drug administration.

During treatment, patients will attend weekly study visits. At the study visits, AE collection, physical examinations, clinical disease assessments (EASI, IGA, BSA, and PP-NRS), vital sign assessments, PK evaluations, and clinical laboratory evaluations will be performed as detailed in the Schedule of Events (Table 1). Patients will complete a daily diary recording their dose administration and PP-NRS itch score during the study.

For all study participants, blood samples will be collected for PK analysis according to the sparse sampling approach described in [Section 6.4](#).

Participants who discontinue study medication earlier than Day 28 will have an Early Termination (ET) Visit at the time of study medication discontinuation and will return for a PTFU Visit, 2 weeks (± 3 days) after the Day 28/ET Visit (see [Table 1](#)).

4.1.3 *Follow-up Period*

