APPENDIX 2 - PATIENT INSTRUCTIONS

Preparation and General Instructions:

1. Reminder to:
 - a) Refrain from bathing, swimming and/or participating in strenuous exercise that would cause profuse sweating for 6 hours after application of study medication.
 - b) Refrain from applying moisturizers, emollients, and sunscreen to AD treatment areas for the duration of protocol therapy. Moisturizers, emollients, and sunscreens may be applied to non-AD treatment areas.
 - c) Refrain from excessive sun exposure (e.g., sunbathing and/or tanning salon visits) and minimize sun exposure (e.g., wear sun protective clothing, hat) as much as possible.
2. Gather a clean washcloth and towel, the study medication bottle, and dropper.
3. Skin should be clean and dry before applying study medication.
4. Wash your hands with soap and water before and after using this study medication.
5. Record your 'worst' itch over the previous 24 hours on your diary in the morning before applying study medication.
6. Apply a thin layer of study medication to the identified AD target skin area as instructed by the study doctor or the study staff. Keep applying study medication to the area throughout the study, even if the skin begins to clear. If new areas of AD appear, study medication may be applied to these areas.
7. Avoid study medication contact with the eye.
8. You will apply study medication twice a day, approximately 8 to 12 hours apart.
9. Document on your diary whether you completed the morning and/or evening dose and total amount of drug (mL) applied at each application timepoint.
10. Remember to bring your study medication bottles both used and unused to each study visit along with your diary.

Study Medication Application:

1. Draw up exactly 1 mL of study medication into the dropper. The medication level should be at the 1-mL line.
2. During study medication application, avoid any study medication running into your eyes.
3. Squeeze a few drops of study medication onto the center of the identified target AD area and gently rub the study medication into your skin. Keep applying a few drops and rubbing into your skin until **the entire area** is covered with a thin film of study medication.
4. Draw up additional medication 1 mL at a time to cover the entire AD area. No more than a total of 8 mL should be used to treat all affected areas. Less than 8 mL may be used if a lower amount is sufficient to cover all affected skin areas.

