| QuantiFERON® Tuberculosis Gold Test   | X         |                  |                  |                   |                      |                   |
| Randomization   |           | X                |                  |                   |                      |                   |
| PK sample   |           | X                | X                | X                 | X                    |                   |
| Fitzpatrick skin type assessment  | X         |                  |                  |                   |                      |                   |
| EASI    | X         | X                | X                | X                 | X                    |                   |
| IGA   | X         | X                | X                | X                 | X                    |                   |
| BSA   | X         | X                | X                | X                 | X                    |                   |
| PP-NRS    |           | X                | X                | X                 | X                    |                   |
| Photography   | X         | X                | X                | X                 | X                    |                   |
| Dispense study drug and patient diary   |           | X                | X                | X                 |                      |                   |
| Study drug instruction, first administration, and observation                   |           | X                |                  |                   |                      |                   |
| Study drug administration (by patient)                              |           | X                | X                | X                 | X                    |                   |
| Collection of study drug, patient diary review, including medication compliance |           |                  | X                | X                 | X                    |                   |
| AE assessment    | X         | X                | X                | X                 | X                    | X                 |
| Prior and concomitant medication review   | X         | X                | X                | X                 | X                    | X                 |

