### 8.4. Randomization

At Visit 2, in the morning of Day 1, eligible patients will be randomly assigned in a 1:1 ratio via an interactive voice/web response system (IXRS) to ATI-1777 or vehicle treatment.

Enrolled patients will be allocated a unique patient number in a sequential order by trial site. Following randomization, Aclaris will provide all study medication in a packed and labelled kit, and the IXRS will identify the kit number to be dispensed to the patient at each relevant visit according to the treatment assigned in the randomization schedule.

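### SAP 12.3.2 counts dosed days, not applications, for a twice-daily product: half-dosing can score 100% and the >120% limit can never be reached.

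*SAP*

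**What the plan says.** The protocol (Treatment Period, under 4.1) has patients apply study drug "twice daily for 28 days to target areas affected by AD". Section 7.4 splits this into a morning application and a second one 8 to 12 hours later. The patient instructions in Appendix 2 ask for each half of the day separately: "Document on your diary whether you completed the morning and/or evening dose", together with the volume in mL at each application.

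SAP 12.3.2 builds the compliance percentage from that diary. The numerator is the number "of days patient reported taking study drug" and the denominator is the number "of days patient was in the study". It adds: "Days with missing patient diary data will not be included in the calculation above". Results are grouped in categories that run from below 80% to 120% and above. The flag follows: "Major non-compliance is defined as compliance < 80% or compliance > 120" (per cent). Bottle weights are listed but do not enter the percentage or the flag.

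SAP 12.1.2 names non-compliance with study drug in a guideline list of important deviations. SAP 9.2.2 removes patients with certain major deviations from the Per-Protocol (PP) set, and SAP 12.4.3.5 uses the PP set to test sensitivity to compliance.

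**The concern.** The numerator and denominator are both days, but the thing to be measured happens twice a day. The SAP does not say that a day counts only when both applications were made. On the plain reading, any use on a day makes it a full day, and the percentage cannot tell one application a day from two.

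The limits do not suit the formula either. A category at 120% and above, and a criterion of more than 120%, belong to a measure that can exceed 100%. A ratio of dosed days to counted days cannot.

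At stake are the compliance summary by treatment group and the SAP's only numeric definition of major non-compliance. That definition could also inform the review of important deviations and, through it, membership of the PP set, whose stated purpose includes testing compliance.

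**Working it through.** The SAP gives no calculated compliance figure to reproduce, so the check is which values the stated formula can produce.

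**Inputs**
- 2 applications a day for 28 days (protocol 4.1.2 and 7.4): 2 × 28 = 56 planned applications. Two on Day 1 are feasible, because SAP 8.4 places randomization in the morning: "At Visit 2, in the morning of Day 1, eligible patients will be randomly assigned in a 1:1 ratio".
- Flag limits of <80% and >120% (SAP 12.3.2).
- Assumptions: the denominator is the 28-day Treatment Period; the diary is complete, so no day drops out; a day with one application counts as a day of taking study drug.

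**Formulas**
- SAP score = 100 × dosed days / counted days.
- Share of applications = 100 × applications made / 56.

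**Half-dosing**

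| Pattern over 28 days | SAP score | Flag at <80%? | Share of applications |
|---|---|---|---|
| Two a day, every day | 28/28 = 100% | no | 56/56 = 100% |
| One a day, every day | 28/28 = 100% | no | 28/56 = 50.0% |
| One a day on 23 days | 23/28 = 82.1% | no | 23/56 = 41.1% |
| One a day on 22 days | 22/28 = 78.6% | yes | 22/56 = 39.3% |

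**Upper limit.** Every dosed day is also a counted day, so dosed days ≤ counted days and the maximum is 100%. Listing every possible count for periods of 1 to 45 days confirms this. The ≥110% to <120% and ≥120% categories are always empty, and the ≥100% to <110% category can hold only exactly 100%. Fixing the denominator at 28 days, which the SAP does not do, would not rescue the limit. A Day 30 visit (the late end of the ±2-day window) gives 30/28 = 107.1%, and exceeding 120% needs 34 days of use (34/28 = 121.4%).

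**Does another reading of a dosed day help?** Suppose a day counted only when both applications were made. A once-daily user would then score 0/28 = 0% instead of 50%. A patient who missed one application on each of 6 days would score 22/28 = 78.6% and be flagged, despite 50/56 = 89.3% of applications. This reading also misstates twice-daily use.

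**Does the period matter?** The denominator period is not defined. The missing-diary rule and the visit schedule, where the row "Collection of study drug, patient diary review, including medication compliance" is last marked at Day 28/ET, probably confine it to treatment. If it ran to Day 42, a fully adherent patient would score 28/42 = 66.7%. One and two applications a day would still score the same, and 100% would still be the ceiling.

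**The case against.** The strongest reply concerns consequence. No passage links the 80% flag to the PP set. SAP 12.1.2 is a guideline list that cites neither the formula nor the 80% limit, SAP 9.2.2 leaves major deviations to be defined before unblinding, and protocol 9.2 defines the PP population by a recorded Week 4 EASI score. A reader might infer that half-dosers are necessarily kept in the PP analysis, or that the primary result is biased. The documents support neither: PP exclusion is left to a later decision, and the primary analysis uses the FAS whatever the compliance.

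Under-use can also surface elsewhere. Protocol 7.8 calls for diary review, documentation of missed doses, bottle weighing and eCRF recording of departures from correct use. That stands, but SAP 12.3.2 uses none of it in the percentage or the flag.

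The void upper limit alone changes no result: two categories print as empty and one criterion never fires. That also stands. It leaves over-use undetected by the flag.

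A reader might also treat the undefined period, or the lack of a rule for interrupted days, as errors of the same kind. They are missing detail. The main result does not depend on them.

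Finally, one could count 55 applications, because drug is collected at the Day 28 visit. The protocol's 28 days of twice-daily use gives 56, and the Day 28 sampling text for PK Subgroup 3 refers to a later application. With 55, the two shares would be 28/55 = 50.9% and 23/55 = 41.8%, and the conclusion is the same.

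**Conclusion.** The point holds as a fault in a stated derivation. On the plain reading, 50% of planned applications is reported as 100% compliance, and as little as 41.1% passes the 80% limit on a 28-day base with a complete diary. The >120% limb and the two categories from 110% upward cannot be met, and this holds whichever way the days in the study are counted.

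The damage is to the compliance table and the numeric flag. An effect on important deviations or the PP set is possible but conditional on decisions that the SAP leaves open, and the primary FAS comparison is untouched. The change should be made because the summary would otherwise be wrong for a twice-daily product and the correction is cheap.

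**What to change.** In SAP 12.3.2, before unblinding:

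- Define compliance as 100 × applications recorded in the diary / applications scheduled over the patient's Treatment Period, at two a day, up to the last scheduled application or permanent discontinuation of study drug.
- State that on a day with any diary entry, an application not recorded as made counts as not applied. Only days with no diary data at all are left out of numerator and denominator, in line with the SAP's present rule. Without this, a morning-only user with blank evening entries could again score 100%.
- Apply the <80% limit to this measure. On 56 scheduled applications, 45/56 = 80.4% is not flagged and 44/56 = 78.6% is; once-daily use, at 50.0%, is flagged.
- Delete the >120% limb and the categories from 110% upward, or base an upper limit on a measure that can exceed 100%. With only a morning and an evening entry each day, the new measure also stops at 56/56 = 100%, whereas >120% would need 68 applications (68/56 = 121.4%).

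The cost is derivation text and programming, since the diary already records morning and evening doses. Reported compliance may be lower, partly because an application made but not written down on an otherwise completed day will count as missed. No dosing rule changes.
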